Milestone 1: NF loci (dACC or amygdala) must show higher activity during ESF-NF and higher FC with mPFC after NF training during the ESOM or ER tasks with effect sizes of $d \geq 0.4$.

Milestone 2: 20% of variance in psychological target's change (ETB, IAT) must be associated with amygdala or dACC to mPFC FC changes during the ESOM or ER tasks after NF.

If those milestones are met, during **the R33 phase**, 70 suicide attempting participants with pre-NF assessments will be randomized 1:1 to: NF or NF from a region that is not related to memory recall, labeled as "Unrelated-NF". Participants will be matched in sex, age, IQ, illness severity, suicide ideation, and abuse history if possible. Leveraging Bayesian methods to increase power, our aims and hypothesis (**H**) for the R33 phase are:

R33 Aim 1. Confirm target engagement in the NF versus the Unrelated-NF group.

H1.1: Right amygdala or dACC activity will be higher for active versus Unrelated-NF.

H1.2: Right amygdala or dACC – mPFC FC will be higher during self-processing and affect regulation tasks following active NF compared to Unrelated-NF training sessions.

R33 Aim 2. Test the relationship between neural and psychological targets' engagement and suicide ideation. H2.1: Lower affect dysregulation and abnormal self-processing behavior will follow active NF as compared to Unrelated-NF, mediated by amygdala or dACC to mPFC FC changes in self-processing and affect regulation tasks. H2.2: Higher amygdala or dACC to mPFC FC after NF will be associated with lower suicide ideation. H2.3: Affect dysregulation or abnormal self-processing behavioral changes will mediate the association between changes in FC and suicide ideation before versus after NF.

2. Background

Suicide is the 2nd leading cause of adolescent death in the U.S ²¹. Yet it is increasingly acknowledged that current evidence-based interventions for illnesses linked to suicide ideation and attempts underperform across the lifespan ^{1-7,22}.

3. Study Endpoints/Events/Outcomes

3.1 Primary Endpoint/Event/Outcome:

The primary outcome of the R61 stage will be the fMRI imaging results, behavioral tasks (IAT and EBT) and self-reported suicide ideation data. The DERS²³, RD¹²⁰ and the SPPA^{24,25} will provide self-report measures of affect dysregulation and abnormal self-processing. **The primary outcomes of the R33 stage** are similar as above but now include the C-SSRS⁹⁸ and SIQ²⁹ to test changes in suicide ideation and attempts

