R33 phase. We anticipate screening **~700** contacts for MRI eligibility over 3 years in the R33 phase. We expect that approximately **300 Participants may** perform baseline evaluations and pre-treatment tasks and to garner **~90** high quality scans for all NF sessions randomly assigned to active (**dACC or Right-Amygdala** depending on research phase) versus Unrelated-NF. **70** (minimal number for analysis) and complete pre and post NF-training phenotypical data and high-quality NF scans.

12. Local Recruitment Methods

12.1 Recruitment Process:

We will seek referrals from the Adolescent Inpatient Units at the University of Minnesota (U of M) MHealth Fairview, from the Washburn Children's and Fairview Clinics, the Minneapolis School Clinics, Children's Hospitals and the Emily Program as well as other mental health institutions in the Twin Cities area including Emergency Rooms. Clinicians within inpatient units will extend brief permission to contact forms to participants or their parents. Clinicians can also point out parents or participants to a Quick Response (QR) code that will trigger a permission to contact the used phone number to initiate the screening process. This method is particularly important to protect clinicians, participants and their family and the research staff from in person close contact in closed units to avoid contagion related to epidemics or other contagion agents.

Clinicians can inform research staff about specific patients that are suitable for research and research staff will then extend the permission to contact to the adolescent or their parents/caregivers. Clinicians will not explain the research in detail beyond what will be posted in the permission to contact forms or flyers. Instead, the contact forms or the **Quick Response (QR) code** will give researchers permission to call parents or Participants and explain the research over the phone and schedule an in-person or remote video call consent process. Additionally, individuals that might extend permission to contacts or use the Quick Response (QR) code include ER staff, doctors, therapists, social workers, pediatricians, or teachers. Both research staff and other referring personnel that extend permissions to contact or Quick Response (QR) code prompts will limit the effects of coercion by ensuring that patients and their caregivers understand that:

1st their decision to participate or not does not affect the quality or availability of care.

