25.9 Adults Unable to Consent: NA

Adolescent participants aged 18+ that are not able to consent or that demonstrate lack of understanding of research via the UBACC will be excluded or staff will endeavor to correct their understanding of research versus clinical provision of services and other characteristics of research endeavors.

26. Setting

26.1 Research Sites:

Participants will be identified in in-patient units and emergency rooms around the Twin Cities, including those in the Fairview U of M Clinic. Research procedures will be conducted at the U of M center for magnetic resonance research (**CMRR**) and at the U of M department of psychiatry.

26.2 International Research:

- NA

27. Multi-Site Research

- NA

28. Coordinating Center Research

28.1 NA

29. Resources Available

29.1 Resources Available:

During the 2-year R61 phase, we anticipate screening ~120 participants using standard MRI eligibility questions and screening for suicide ideation and attempts. A minimum of 56 participants will undergo baseline tests and pre- NF training tasks over 2 years. Historically, we have obtained fMRI and structural data with stringent criteria of signal-to-noise ratio and movement (i.e., displacement <0.2 mm) in ~90 % of participants in the target age range and disorders. Some attrition is expected due to movement and treatment discontinuation. We anticipate garnering good quality scans for all NF sessions in ~50 participants over 2 years randomly assigned to dACC or Right-Amygdala NF-Training. We budgeted for additional repeat scans to recover lost data if needed. We expect that 40 participants will complete all post-NF assessments and 1-month follow-up assessment, yielding 20 data sets per NF target with high quality scans and pre and post NF training data in the R61 phase.

We anticipate screening ~290 contacts for MRI eligibility over 3 years in the R33 phase. We expect to perform 100 baseline evaluations and pre-treatment tasks and to garner ~90 high quality scans for all NF sessions randomly assigned to active (dACC or Right-Amygdala depending on research phase) versus Unrelated-NF. Of those we anticipate at least 72 will complete the post-NF training phenotyping and 1-month follow-up. We have budgeted for repeat scans per year to obtain 70 complete pre and post NF-training phenotypical data and high-quality NF scans.

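### The R33 phase uses 70 both as the number randomised and as the number with complete data; randomising 70 would leave about 50 to 56, and the number to be randomised is not otherwise stated

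*Combined protocol and SAP*

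**What the plan says.** Section 1 (Objectives) states that "70 suicide attempting participants with pre-NF assessments will be randomized 1:1" to active NF or to NF from an unrelated region. Here 70 is a count at randomisation, among people who have done the assessments that precede training.

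Section 11.1 (R33 phase) allows for about 300 baseline evaluations and expects "to garner ~90 high quality scans for all NF sessions randomly assigned to active" or unrelated NF. It attaches these words to the number 70: "minimal number for analysis) and complete pre and post NF-training phenotypical data and high-quality NF scans".

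Section 29.1 (Resources Available) gives a fuller flow. "We expect to perform 100 baseline evaluations and pre-treatment tasks"; about 90 then have good scans for all NF sessions; "Of those we anticipate at least 72 will complete the post-NF training phenotyping and 1-month follow-up"; and finally "We have budgeted for repeat scans per year to obtain 70 complete pre and post NF-training phenotypical data and high-quality NF scans". It also says that usable imaging data have historically been obtained "in ~90 % of participants in the target age range and disorders".

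Section 18 gives no R33 sample size, power statement or analysis population. The missing-data paragraph in Section 5.1 allows unrecoverable data to be imputed (mean values are one option) or removed, with the choice left to the time of analysis.

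**The concern.** The same number marks two different points in the participant flow: randomisation in Section 1, and what remains after scan loss and drop-out in Sections 11.1 and 29.1. A team that follows Section 1 and stops at 70 randomised would, on the plan's own expectations, finish well short of the minimum it sets for analysis.

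The gap between those randomised and those with complete data also matters because no R33 analysis population is named. The Columbia scale (C-SSRS) and the Suicide Ideation Questionnaire (SIQ) are among the R33 primary outcomes in Section 3.1. Section 14.1 withdraws, at least temporarily, participants who are hospitalised or at imminent risk of an attempt, so loss could be related to the outcome. If only complete cases were analysed, the comparison would no longer be between the groups as randomised.

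**Working it through.** **Inputs.** Section 1: 70 randomised 1:1. Section 11.1: 70 as the minimum for analysis. Section 29.1: 100 baselines, about 90 with good scans for all NF sessions, at least 72 completers, 70 complete data sets, and a usable-scan rate of about 90%.

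**Reproducing the plan's flow.**
- 100 x 0.90 = 90, the stated number with good scans.
- 72/90 = 0.80. The R61 figures in Section 29.1 give the same rate: 40/50 = 0.80.
- 90 x 0.80 = 72, the stated number of completers.

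Section 29.1 is therefore coherent, with two losses applied in sequence: 0.90 for scans and 0.80 for completion.

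**If 70 are randomised, as in Section 1.**
- Completion loss only: 70 x 0.80 = 56 (28 per arm), which is 14 below the minimum.
- Both losses: 70 x 0.90 x 0.80 = 50.4, about 20 below it.

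**Where the figure of about 90 belongs.** In Table 1 the NF sessions are on scan days 1 and 2. Whether a participant has good scans for all of them is known only after allocation and scanning, so about 90 is a count after randomisation.

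**Number to randomise for 70 complete data sets.** 70/(0.90 x 0.80) = 97.2. This is close to the 100 people whom Section 29.1 expects to complete baseline and pre-treatment tasks, the state in which Section 1 places participants at randomisation.

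**Share without complete data.**
- From 97.2 randomised: 1 - 70/97.2 = 28%.
- From 100 randomised: 1 - 70/100 = 30%.
- Counted only from the 90 with good scans: 1 - 72/90 = 20% to the completers, or 1 - 70/90 = 22% to the complete data sets.

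**Illustration of precision.** Assume a two-sided alpha of 0.05 and a two-sample t-test. The plan has neither for R33, which is Bayesian. The effect detectable with 80% power is about 0.68 SD at 35 per arm and 0.76 SD at 28 per arm.

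**The case against.** The best defence is that 70 is a floor, not a cap. Repeat scans are budgeted to recover lost data, Section 5.1 permits imputation, Section 15.2 keeps data collected before termination, and Section 14.1 lets hospitalised participants return. This stands to a point: nothing in the plan prescribes excluding non-completers. A reader might infer that the plan defines its R33 analysis set by completion and scan quality. The documents support only the weaker statement that no set is defined and that elimination is one permitted choice.

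A reader might also infer that about 90 are randomised, 45 per arm, with 22% dropped afterwards. The documents do not establish this, because those 90 already have good scans for every NF session. Writing 90 into Section 1 would recreate the shortfall: 90 x 0.90 x 0.80 = 64.8, below 70.

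Nor do the documents show that loss follows severity or differs by arm. Both are possible; neither is known.

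Finally, the R33 hypotheses on ideation (H2.2 and H2.3) are built on change in functional connectivity (FC) and need imaging data, so a complete-scan set is reasonable for them. That is accepted. It does not settle the number randomised, or which participants any comparison of SIQ or C-SSRS between arms should include.

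**Conclusion.** The contradiction is in the current text and does not depend on any power assumption. Seventy cannot be both the number randomised and the number with complete data when the plan itself expects losses in between. Under Section 1, about 56 would remain on completion loss alone and about 50 after both losses, against a stated minimum of 70. The number to be randomised is not given consistently anywhere. The plan's own rates imply about 97, with about 28-30% of those randomised lacking complete data.

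This rests on three assumptions: the rate of about 90% applies to scans across all NF sessions, as 100 to 90 suggests; the 72/90 completion rate carries over to whatever number is randomised; and essentially all who finish the pre-treatment tasks are randomised. Successful repeat scans would reduce the loss. The detectable-effect figures are illustrative only.

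**What to change.** - In Section 1, replace 70 randomised with about 97 to 100 randomised 1:1, to yield at least 70 complete data sets. State when randomisation takes place.
- Align Sections 1, 11.1 and 29.1 on one flow: baselines, randomised, good scans, completers, complete data sets. Resolve the R33 baseline counts, about 300 in Section 11.1 against 100 in Section 29.1.
- In Section 18, specify that any comparison of SIQ or C-SSRS between arms uses everyone randomised, by assigned arm, in a likelihood-based or Bayesian repeated-measures model. SIQ is scheduled at Visits 1 to 5; C-SSRS only at Visits 1, 4 and 5. For these comparisons, this replaces the open choice in Section 5.1 between imputation and elimination.
- Limit the complete-scan set to the hypotheses that need imaging data (activity, FC and mediation), and report exclusions by arm with reasons.

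The cost is protocol and SAP wording and a modest amount of extra analysis. No participants are needed beyond the 100 baselines already in Section 29.1.

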Description. Neurofeedback training is a modality of biofeedback. During neurofeedback training, a person that is inside the scanner can see the changing levels of activity of a selected brain region. Because regional neural activity is visually displayed to a person in the scanner, this enables voluntary modulation of neural activity in regions of interest, which can trigger corrective neuroplastic processes. We will deliver neurofeedback training using the **Emotional Self-Face Neurofeedback, ESF-NF paradigm**^{30,31} comprised by four ~7.33 min NF training runs preceded by a 5 min baseline (ESF no NF), a 5 min practice run, and followed by a 5 min transfer run (ESF no NF)³². Training entails NF blocks paired to a self-happy face visual that signals the start of NF. There will be two control conditions to distract participants from contemplating positive memories and dampen affect regulation and self-processing networks. During one control condition participants will count backwards from 100 cued by an unfamiliar happy teen face with no NF (count backward = **CB**). During other control condition participants are presented with the cue "Rest" and are asked to relax and look at the screen (**Rest**). During **NF**, participants will attempt to increase neural activity displayed via a colored bar shifting up or down depending on values provided by MURFI2 software³³. Green = Activity > baseline and red = Activity < baseline. We may adapt the feedback procedures to be more like a game, but the current description still conveys the visual feedback modality. The active NF loci will be the right amygdala or the dorsal ACC in the R61 phase. The active NF loci during the R33 phase will be the loci of higher engagement that best elicits functional improvements in the R61 phase. As in prior NF trials³⁴⁻³⁶, participants select positive autobiographical memories that they recall during NF training. **[name]** has administered a short version of the proposed task to 53 Participants^{30,31}. ROIs for the dACC, right amygdala or an unrelated site (e.g., the left intraparietal sulcus) will be localized from coordinates mapped to each participant's structural image. **[name]** has used this software and protocol with healthy and depressed participants^{30,31}. The scanning room and specifically the scanner coils already include devices to present stimuli. It is part of the hardware. We may monitor heart rate and breathing using devices that are superficially attached to the participant's torso. These devices are also often used as part of scanning procedures of human participants.

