Emotional Self-Other Morph (ESOM) task^{41,42}. Before and after NF training, participants will identify their own or another teen's face with happy, neutral, or sad expressions via button press in the scanner. Faces (N=150) are presented against a black background and drawn out of 21 possible composites (5% increments) that range from 0% self and 100% other or 100% self and 0% other. We have published that ACC and mPFC activity and ACC-right amygdala functional connectivity during self vs. other-face recognition distinguishes adolescent suicide attempters vs. both depressed and healthy participants^{41,42}. This supports our decision to employ the ESOM task to test the engagement of circuitry of self-processing and affect regulation (right amygdala or dACC-mPFC FC) after neurofeedback training. The current version of this task has been programmed in E-Prime.

Emotion Regulation (ER) task. This task resembles a task used to modulate affect via NF in BPD patients⁴³. It entails viewing 3 blocks of emotional images (2 negative and 1 positive) and 1 block of neutral images (image blocks duration = 70 secs, task time~13 min). Participants will increase their positive affect during positive and neutral blocks and decrease their negative affect during negative blocks in a "regulate" condition using any regulatory strategy of their preference. During a "passive" condition they will observe the images naturalistically. Standard images are drawn from the International Affective Pictures System^{44,45}. Self-injury images were gathered from pictures participants have posted online⁴⁶. Our data on image ratings indicated that all participants rated such images similarly. Participants will report affect regulation strategies used and rate images on a scale of 1-5 for arousal and valence after the scanning session. [name] has administered this task to healthy and self-injurious participants⁴⁷. As noted in our pilot data section, it yielded significant amygdala-cortical FC differences for self-injury versus negative images between healthy and self-injurious participants. The current version of this task has been programmed in E-Prime.

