A password protected database of the participant's facial pictures and linking their identifying information to their **ID** numbers will be kept in a secure **AHC** server or Box Secure Storage at the department of psychiatry. Direct identifiers will be necessary to maintain contact with the participant in order to schedule appointments and follow-ups. Specifically, the subject's full name, date of birth, race and ethnicity, address, phone numbers and emails will be kept in our secured subject database in a secure **AHC** psychiatry server. This is necessary so we can make sure we are not asking for consent from the same person more than once for the same study. Video of the assessments will be recorded for scoring purposes and kept in a secure **AHC** server or in a secure physical location. Specifically, **CD's** or **external drives** will be kept in a locked room at the Department of Psychiatry. Pictures of the subject are taken to be used during the MRI task and are also kept in the secure psychiatry or **AHC** server. Members of the research team will be the only ones to view pictures and videos. Pictures of the subjects may be used during the **MRI ESOM** and neurofeedback tasks for future participants and research, if the participants provide approval in the consent and assent forms. **Electronic records** will be kept in password protected computers, drives, servers and/or e-documents. Additionally, written, or digital protocols/instruments/tasks will be identified with the participant's number and no identifying information will be kept in written or protocols/instruments/tasks. Participants will be advised that there will be limits to their confidentiality and that if suicide attempts immediate risks are suspected, or if child abuse or of vulnerable adults or risks of homicide are discovered there would be a need to contact the appropriate organizations and that their parents would be informed.

21. Provisions to Monitor the Data to Ensure the Safety of Participants

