Protecting Privacy: Each participant will be assigned a random, unique identification number. This ID number will be used on all files throughout the database. The participant identification number, rather than participant names, will be placed on all forms to preserve confidentiality. Data from interviews and questionnaires will be collected by members of the clinical assessment team. The project manager or research staff recording online interviews will be responsible for immediate transfer of the data from their temporary device or terminal or study device to the secure storage area, and of entering the data to a secure on-line database. All data will be identified and labeled only by participant ID numbers and will be stored separately from the identifying information and from consent and assent forms. Identifying personal information data such as faces and links between participant's ID's and their personal information will be kept on a **secure server** at the department of psychiatry at the UMN or a Box Secure Server created for the current study and only the study staff will have access to the server. De-identified data will be also stored at the **Minnesota Super-Computing Institute (MSI)** or in **DVD's or external drives that will be kept in locked rooms in secure locations at the Department of Psychiatry**. This includes video-

taped remote research or in-person sessions that were videotaped via Zoom, in person, or some other remote online platform. The PI will consult with MSI engineers to store videotapes of sessions with participants in MSI in the safest, most secure way possible.

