To allow participants proper time to adjust to the environment of an MRI scanner before the actual scanning intervention, we will use a mock MRI scanner.

University of Minnesota Medical Center (UMMC) Child and Adolescent Psychiatry Clinics and Hospital Services. UMMC Psychiatry Clinics provide comprehensive psychiatric care for children and Participants with a broad range of psychiatric disorders. Specialty clinics include the Child and Adolescent Mood Disorders Clinic, and the Child and Adolescent Anxiety Disorders Clinic. [name] and her study clinician team are integrated with and in proximity to all these services which facilitates the timely recruitment of the target sample of Participants and young adults exhibiting suicide ideation or behavior. Just two floors above the PI and research staff's offices in the Department of Psychiatry, is a 25-bed inpatient Adolescent Crisis Stabilization Unit. Many of the patients there were referred to [name] K01 and NARSAD study with the help of the unit staff. The study successfully recruited approximately 130 depressed Participants in Minnesota.

The Institute of Child Development (ICD). Housed in the Department of Child Psychology at the University of Minnesota, ICD has been a premier center of scholarship, teaching, and outreach devoted to the understanding and fostering of child development since it was founded in 1925. Coursework and research activities focus primarily on the central cognitive, social, emotional, and psychological processes that underlie the development of infants, children, and participants. From its inception, a key tenet of the Institute has been to "give away" child psychology. This philosophy has created an environment rich with collaborations, new ideas, and exciting interdisciplinary work.

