City of Minneapolis School Based Clinics. The Minneapolis Department of Health and Family Support (health department) School Based Clinics Program (SBC) provides comprehensive, accessible, teen-friendly health care to Participants. The SBC offers its students easy access to primary care and mental health services because the clinics are located where teens spend most of their day: in school. SBC Director of Mental Health Services, [name] M.A. LMFT, and the other SBC therapists, will work with [name] and her research staff to recruit students 11-18 years old exhibiting suicidal ideation or past suicide attempt that attend the six high schools that have an SBC. [name] has had ongoing recruitment collaboration with [name] and the SBCs over the past several years during her K01 adolescent depression study.

The Washburn Child Center. The Washburn Child Center is a leader in helping children with social, emotional, and behavioral problems and their families, serving children from birth to age 18. They have over 130 years of experience in assisting high risk children in the Minneapolis area. As a community mental health center focused on children's mental health, Washburn Child Center strives to integrate innovative research into program practice, implement meaningful evaluation methods and provide effective training and consultation for agency staff and community collaborators. The PI has an active collaboration with Washburn Child Center and their Clinical Director, [name], who has contributed to her success recruiting 65 depressed participants for her K01 study on adolescent depression. Washburn Child Center will be an excellent source of continued collaboration and source of recruitment for this study.

Prairie Care. Prairie Care is a large provider of mental health services in the state of Minnesota who receives thousands of Participants and young adults, many of them in partial or full hospitalization due to suicide attempts or suicide related acts. [name], MA, LP is a clinic supervisor and therapist there with whom the PI has collaborated with in the past for recruitment. The PI has maintained

an active collaboration with Prairie Care now for 4 years and they have been a steady source of referrals for research. Prairie Care is still growing in the state of Minnesota and the spread of their services will likely double within the next year or two.

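### Clinical participants' photographs may be shown to later participants despite a statement that only the research team views them, with no stated source or familiarity check for the comparison face

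*Combined protocol and SAP*

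**What the plan says.** **The comparison face.** Section 4 describes the CB control condition of the neurofeedback task, in which "participants will count backwards from 100 cued by an unfamiliar happy teen face with no NF". In the ESOM task (Section 5), "participants will identify their own or another teen's face with happy, neutral, or sad expressions via button press in the scanner". The requirement that the face be unfamiliar is written for CB only.

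**Who sees the photographs.** Facial photographs are collected at Visit 1 (study item table, Section 5.1, item 4). Section 20 says: "Members of the research team will be the only ones to view pictures and videos". The next sentence allows participants' pictures to be used in the ESOM "and neurofeedback tasks for future participants and research, if the participants provide approval in the consent and assent forms".

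**Status of a face.** Section 22 refers to "Identifying personal information data such as faces and links between participant's ID's and their personal information". Section 21.1 gives faces as an example of personal health information, and Section 20 restricts access to such files to the research team.

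**Where participants come from.** Section 12.1 says: "We will seek referrals from the Adolescent Inpatient Units at the University of Minnesota". It adds clinics, school clinics and emergency rooms in the same metropolitan area. Section 29.1 adds that two floors above the study offices "is a 25-bed inpatient Adolescent Crisis Stabilization Unit", and that school-based clinic staff will help to "recruit students 11-18 years old exhibiting suicidal ideation or past suicide attempt that attend the six high schools that have an SBC".

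**The concern.** The two sentences in Section 20 cannot both be followed as written. If a consenting participant's picture is used as a stimulus for a later participant, someone outside the research team has viewed it. By the plan's own classification, that person has been shown identifying data.

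This matters because the pool is local. Adolescents from the same ward or school may know one another, and a viewer who recognises the face may learn that a peer took part in a study built around suicidal behaviour. One recognition is enough to cause that harm.

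The secondary issue is measurement. The CB cue is meant to be an unfamiliar face. If the viewer knows the person, the cue carries content that the design intended to leave out. The ESOM self-versus-other comparison could likewise become self versus acquaintance for that viewer.

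**Working it through.** The documents state no figure on this point, so there is none to reproduce. The check is textual, with one illustration.

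**1. Does the plan allow the exposure?** Yes. Section 20 permits reuse in the ESOM and neurofeedback tasks for future participants, on one condition: approval in the consent and assent forms. That condition concerns the person pictured. It says nothing about whether the viewer knows that person.

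**2. Is there a safeguard elsewhere?** Sections 4 and 5 do not say where the comparison face comes from. No passage asks the viewer whether the face is known, or says what to do if it is. The confidentiality risk in Section 16.1 (item 3) and the confidentiality protection text later in Section 16 do not mention recognition by another participant.

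**3. Which analyses use the face?** From Section 18:

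| Contrast | Uses a comparison face? |
|---|---|
| NF vs CB (activity) | Yes, as the CB cue |
| NF vs Rest (activity) | No |
| ESOM, self vs other (connectivity) | Yes |
| ER, regulate vs passive (connectivity) | No |

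Milestone 1 (Section 1) accepts its connectivity component on the ESOM or the ER task.

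**4. Illustration of size.** Let p be the probability that a viewer knows the person shown. The documents do not give p. I assume 0.2%, 1% and 5%, independent between viewers, and one reused face for every later viewer. The last assumption is an upper case, because the plan only permits reuse. With R61 N = 40 there are 40 − 1 = 39 possible later viewers. With R33 N = 70 there are 70 − 1 = 69.

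Expected number of viewers who recognise a face = n × p. Chance of at least one = 1 − (1 − p)^n.

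| n | p | Expected | At least one |
|---|---|---|---|
| 39 | 0.2% | 0.08 | 7.5% |
| 39 | 1% | 0.39 | 32% |
| 39 | 5% | 1.95 | 86% |
| 69 | 0.2% | 0.14 | 13% |
| 69 | 1% | 0.69 | 50% |
| 69 | 5% | 3.45 | 97% |

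At the highest assumed rate, a locus group of 20 would have 20 × 0.05 = 1 affected data set in expectation. The chance of a single disclosure can be appreciable while the expected number of affected scans stays small.

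**The case against.** The case on the other side is substantial, and much of it stands.

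- **Reuse is opt-in and only permitted.** The two sentences in Section 20 can be read as a default followed by a consented exception, and nothing says that participants' photographs are the usual source of the face. This stands. However, the first sentence says that the team will be the only viewers, so the text still needs reconciling, and consent does not control who the viewer is. The consent pages are not in the supplied text, so whether they warn of recognition by peers cannot be checked.
- **Section 4 already requires an unfamiliar CB face.** Showing a known peer there would depart from the plan. True, but no step is given by which staff would know. For ESOM, an unfamiliar other is an inference.
- **Recruitment is wide and slow.** Section 12.1 also lists several clinic networks, advertising and a large mailing, and Section 5.2 allows 5 to 10 years of enrolment. This lowers p but does not remove the overlap.
- **A reader might infer that recognition reveals a suicide attempt.** The documents do not support that. Section 8 also admits depressed youth without past or present ideation, people with borderline personality symptoms whatever their suicide history, and healthy volunteers. What is disclosed is participation.
- **A reader might infer that recognition breaks the ESOM other condition or threatens Milestone 1.** It does not. A known peer is still other, two of the four contrasts use no comparison face, connectivity is tested within participants before and after training, and the R33 arms are randomised with no reason to expect recognition to differ by arm.

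**Conclusion.** The point holds as a minor one, resting on confidentiality. Section 20 promises that only the research team views participants' pictures and then permits their display to later participants. With local recruitment, and with no stated source for the face or familiarity check, following that permission could show an identifiable clinical participant to a peer.

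The statistical consequence is at most a familiarity confound in the NF vs CB and self vs other contrasts of a few participants. NF vs Rest and the ER task are unaffected. The documents give no recognition rate, so any stated percentage of an arm would merely restate an assumed one. The illustration further assumes independent viewers and a reused face for each of them. The conclusion does not depend on it: it needs only the conflict in Section 20, the plan's treatment of faces as identifying, and the overlap in recruitment sources.

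**What to change.** 1. **Section 20:** reconcile the two sentences by stating that clinical participants' photographs will not be used as comparison faces for later participants in this study. Bring the consent and assent wording into line.
2. **Sections 4 and 5:** state that the CB and ESOM comparison faces come from people outside the clinical sample and outside the recruiting clinics and schools.
3. **Before scanning:** ask each participant whether the comparison face is known, replace it if so, and record the answer. Asking before the first ESOM run lets one face be kept for the pre- and post-training runs.

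The source restriction is the part that protects confidentiality. A familiarity question alone would not, because showing a clinical participant's face in order to ask it would already expose that person. The question protects the contrasts.

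The cost is protocol and consent wording, one recorded question, and a modest stimulus set with suitably matched faces sourced elsewhere.
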